Attrition and Retention: Based on prior experience with this population, we anticipate a 15% attrition rate in 12 months. To account for this under an intent-to-treat analysis plan, we increased the sample size for 15% attrition. We will enroll 232 patients (n=58 per group). We intend to minimize drop out from the study by providing monetary compensation for completing the study. In addition, at enrollment, following consent, we will request from every participant, the names, addresses, and telephone numbers of a next of kin who would know how to get in touch with the participant, in the event of a missed appointment.

Patient eligibility criteria: The study inclusion and exclusion criteria are as follows

Inclusion Criteria: 1) Age ≥ 18 years; 2) Clinical diagnosis of T2DM and HbA1c $\geq 9\%$ at the screening visit; 3) Self-identified as Black or African American; 4) Subject must be taking at least one oral medication for diabetes, hypertension, or hyperlipidemia and must be willing to use the MEMS cap and bottle for 12 months; 5) Subjects must be able to communicate in English; and 6) Subjects must have access to a telephone (landline or cell phone) for the 12 week intervention period.

Exclusion Criteria: 1) Mental confusion on interview suggesting significant dementia; 2) Participation in other diabetes clinical trials; 3) Alcohol or drug abuse/dependency; 5) Active psychosis or acute mental disorder; and 5) Life expectancy < 6 months.

Description of Intervention: The proposed separate and combined diabetes education and behavioral skills training intervention are based on the information-motivation-behavioral skills model and provide information, motivation, and behavioral skills training. The interventions will be delivered via weekly telephone calls over a 12-week period by trained diabetes educators. Two full-time diabetes educators will deliver the interventions. Each full-time educator will only be responsible for providing care to subjects in all the four study arms (i.e. knowledge/information, motivation/behavioral skills, combined, or usual care). Diabetes educators will be trained in behavioral skills counseling by study consultant.

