Baseline Visit & follow-up visits: At the baseline visit, the RA will give detailed explanation of the study, the reimbursement schedule, and obtain consent. Subjects will get their blood pressure measured and provide blood specimen to measure HbA1c. In addition, subjects will complete a questionnaire that captures demographics, medical history, HRQOL, physical activity, home blood glucose monitoring, resource utilization, and medication adherence. After the baseline assessment, follow-up assessments will be conducted at 3-, 6-, and 12 months. As much as possible, research visits will be scheduled on the same day as their clinic visit.

Primary Outcome Measure:

HbA1c/Fasting Lipid Profile: Blood specimens will be obtained at baseline, 3-, 6- and 12-months visits by trained phlebotomists. About 10cc of blood will be drawn and sent to the laboratory for HbA1c. Fasting lipids will also be measured at baseline, 3-, 6-, and 12 months.

Patient Randomization Procedures: All subjects who sign an informed consent for the study, meet eligibility requirements and are randomized will be entered into the study database. The research coordinator will collect the pre-specified eligibility information (written informed consent, demographics, eligibility criteria) and enter the information into the study database via the secured study website. Personal health information (PHI), e.g., name, medical record number, social security number, will not be entered into the study database. When all pre-specified information is entered for the patient, the project-specific computer program will confirm the eligibility of that patient. Once confirmed, the computer will generate the intervention assignment based on a pre-programmed randomization scheme. A confirmation report will be generated by the computer and will include the subject's study ID number, assigned treatment date of randomization, basic demographics (age, gender) and eligibility criteria compliance. This report will be filed at the primary center in the confidential study specific files. All registered patients who are screened yet do not get randomized will have specific screening information entered into the study database.

Sample Size and Power

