1. Psychological Distress: Because we will be administering a questionnaire that measures the presence of depression, we will take several steps to ensure the safety of all research participants. RAs will be trained by the PI to identify patients who meet criteria for depression on the PHQ-9. Subjects' who screen positive for depression will be notified during the visit and verbally instructed to seek care from their primary health care provider (PCP). They will also be given the 24-hour MUSC crisis psychiatry telephone service and told to call if they experience acute worsening of symptoms before they can be seen by their PCP.

2. Venipuncture (blood drawing): To reduce the risks of discomfort and bruising, venipuncture will be performed by trained personnel. To reduce the risk of fainting, blood will be drawn while subjects are in a seated position. The amount of blood that will be drawn, approximately 10cc, is not considered to pose a health risk for most adults. .

3. Blood Pressure Measurement: To lessen any associated risks, blood pressure measurements will be performed only by trained personnel utilizing a standardized protocol. Subjects with elevated blood pressure will be advised to contact their primary care provider. Those with potentially life threatening blood pressure readings will be sent to a local emergency room for treatment.

4. Administration of Research Questionnaires: Some participants might be offended by detailed questions about emotional or physical health status and impairment, and healthcare utilization. All participants will be informed at the outset that they may terminate participation at any point. Our past research suggests that data collection using these measures can be conducted without undue psychological distress or exacerbation of symptoms among study participants.

5. Unknown risks: Subject participation in research may have other unknown risks. The researchers will advise subjects if they learn of emerging information that might alter subjects' decisions to participate in this study.

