B. Subjects requiring medical or other professional intervention for study-related events will be provided with appropriate and timely medical guidance by the PI. If adverse events occur during the conduct of this study, they will be reported to the IRB in accordance with the MUSC IRB Adverse Event Reporting Policy. The results of subjects' clinical assessments will be available within a few weeks of their study visit. The principal investigator will review and advise subjects of these results by phone and, at their request; he will also advise their personal physician of the results.

C. To protect against the potential risk of loss of confidentiality and/or breach of privacy, data will be compiled using codes in lieu of personal identifiers. Access to study data will be limited to research personnel. Development of and security oversight for the electronic database for this study will be performed by the study statistician. Paper documents pertaining to this study will be stored in locked file cabinets and electronic data will be entered into secure, password-protected databases developed for this study by the research assistants. The PI will perform periodic review of the data entry process to ensure accuracy of recording. When study results are published or presented, only aggregate reports of the results will be used and participants' identity will not be revealed. A file of name, contact address, telephone number, and other research identification numbers will be stored separately on paper and on computer, for purposes of audit by the sponsor (NIH) and MUSC IRB, if necessary.

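### The PHQ-9 procedure states no staff-initiated, same-day action for a participant found at the visit to be in acute danger, although the blood pressure procedure does

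*Protocol*

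**What the plan says.** The depression procedure is item 1 (Psychological Distress) under Protection against Risk in the Protocol. The trigger is a single one: "RAs will be trained by the PI to identify patients who meet criteria for depression on the PHQ-9". The response is also single. Subjects "who screen positive for depression will be notified during the visit and verbally instructed to seek care from their primary health care provider", and all of them receive the number of a 24-hour crisis psychiatry telephone service and are "told to call if they experience acute worsening of symptoms before they can be seen by their PCP".

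Item 3 of the same list (Blood Pressure Measurement) has two levels. An elevated reading leads to advice to contact the primary care provider (PCP). Above that, "Those with potentially life threatening blood pressure readings will be sent to a local emergency room for treatment".

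Paragraph B, under the same heading, adds a general commitment: "Subjects requiring medical or other professional intervention for study-related events will be provided with appropriate and timely medical guidance by the PI".

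The exclusion criteria, given under both Patient eligibility criteria headings, include "Active psychosis or acute mental disorder". Baseline Visit & follow-up visits says "follow-up assessments will be conducted at 3-, 6-, and 12 months", and on timing, "As much as possible, research visits will be scheduled on the same day as their clinic visit".

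**The concern.** The Protocol names psychological distress among the study's potential risks and refers to this section for how that risk is kept low. The study itself administers the depression questionnaire, and the result is known while the participant is still with the research assistant (RA). The person best placed to act on an acute finding is therefore study staff, at that moment.

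The written procedure leaves every step after notification to the participant, who is to arrange a PCP visit and to call the crisis line if symptoms get acutely worse. For a typical positive screen that is a reasonable pathway. For someone already in danger in the room, it leaves the next move to the person who may be least able to make it. At stake is the safety of individual participants. No estimate, test or sample size depends on it.

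**Working it through.** No arithmetic applies. The check sets the two procedures side by side, looks for another section that supplies the missing step, and then follows one case through the text.

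**1. The two procedures compared**

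- *Trigger.* PHQ-9: one cut, meeting criteria for depression; no severity level and no response to suicidal thoughts is named. Blood pressure: two cuts, elevated and potentially life-threatening.
- *Routine action.* The same for both: the participant is directed to the PCP.
- *Acute action.* PHQ-9: a crisis number for all positives, used by the participant if symptoms worsen acutely before the PCP visit. Blood pressure: the participant is sent to an emergency room because of the finding at the visit.

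The acute actions differ in who starts them (participant or staff) and in when they apply (after later worsening, or at once).

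**2. Whether another section supplies the step**

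- *Protection against Risk, paragraph B.* Guidance from the PI is promised for study-related events. A crisis disclosed during study screening can reasonably be read as such an event. The paragraph does not say who alerts the PI, or that this happens before the participant leaves.
- *Exclusion criteria.* Excluding acute mental disorder decides eligibility. It sets no referral for the person excluded, and it does not cover a state that arises by the 3-, 6- or 12-month visit.
- *Baseline Visit & follow-up visits.* Same-day clinic visits are a scheduling aim, so a clinician cannot be assumed to be at hand.
- *RA training.* The stated content is identifying patients who meet PHQ-9 criteria. Recognising or escalating an acute case is not mentioned.
- *Data and Safety Monitoring Plan.* The internal committee, which includes the PI and a medical monitor, meets quarterly and by telephone when needed. This is oversight, not a response at the visit.
- *Project Timeline.* Setting up patient safety procedures is listed as a Year 1 activity, without content.

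None of these states a same-visit step.

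**3. One case followed through**

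Take a participant who screens positive and tells the RA of suicidal thoughts. An RA who follows item 1 exactly notifies the participant, gives the verbal PCP instruction and hands over the crisis number. The condition for calling is acute worsening. A participant who is already at the worst point and stays there does not meet it. Paragraph B may bring in the PI, but nothing says that this precedes departure. A participant with a life-threatening blood pressure reading would, under item 3, be sent to emergency care.

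**The case against.** The strongest reply is that nothing in item 1 is false or contradictory. It does not bar escalation, and a fuller procedure can always be imagined. That is true of many omissions. This one differs because the Protocol does prescribe a response, and that response, followed exactly, is inadequate for the acute case.

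A second reply is that the blood pressure parallel is imperfect. A reading can itself be life-threatening, whereas the Protocol describes the PHQ-9 only as measuring the presence of depression. This stands in part. Two levels against one shows a difference in drafting and does not by itself prove inadequacy. The parallel does show that the authors regarded same-day action on a visit finding as belonging in this section. The point also does not need the score to identify a crisis, since the participant's own report or appearance can do so.

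A reader might infer more than the text supports, in four ways:

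- *That there is no acute provision at all.* The 24-hour crisis line is one, though participant-initiated and limited to later worsening.
- *That action rests solely on the RA's initiative or on a clinic visit falling that day.* Paragraph B commits the PI to timely guidance for study-related events.
- *That the trial has no escalation procedure.* The Year 1 safety procedures are not shown. Only the Protocol text can be judged.
- *That the number of participants exposed can be estimated.* The Protocol gives no rate of acute cases and does not say at which visits the PHQ-9 is given. A count of screens would say nothing about acute cases.

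**Conclusion.** The point holds in a limited form. Item 1 gives every positive PHQ-9 the same PCP referral and self-call crisis line, and it states no staff-initiated action before departure for a participant found to be in acute danger. The blood pressure item does state such an action. Paragraph B narrows the gap without closing it.

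The size cannot be expressed as a number, and none is offered. The conclusion rests on two assumptions: that RAs work from the Protocol as written, and that a participant in acute danger may be met at some visit. It does not depend on how often the PHQ-9 is repeated. Even at baseline, excluding a person in crisis does not get that person care.

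This is a cheap improvement to participant safety and is worth making. The HbA1c endpoint, power and analysis are unaffected.

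**What to change.** Add one or two sentences to item 1, Psychological Distress. Suggested content: if a participant reports suicidal thoughts or appears in acute crisis at any visit, the RA contacts the PI or the designated medical monitor before the participant leaves, and the participant is assessed or sent to emergency care. Keep the PCP referral and the crisis line for all other positive screens. The investigators may add a severity trigger on the PHQ-9 if they want one; the Protocol gives no basis for choosing its value here.

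The cost is that the PI or medical monitor must be reachable while visits take place and must give some time to acute cases. RA training would need to cover the new step. Both roles already exist in the study, so no new staff or visits are needed.

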3. POTENTIAL BENEFITS OF THE PROPOSED RESEARCH TO THE SUBJECTS AND OTHERS

The intervention is expected to benefit patients, by increasing their knowledge of diabetes, activating and empowering them to better care for their diabetes, improving blood glucose and blood pressure control, and reducing their risk developing complications of diabetes. Patients in the usual care group will benefit by increasing their general health knowledge.

4. IMPORTANCE OF KNOWLEDGE TO BE GAINED

The findings of this study, if successful, will lead to the implementation of this feasible, evidence-based intervention for high risk minority patients with T2DM. The study will provide new information on how to improve quality of care for diabetes in ethnic minorities and reduce the disproportionate burden of diabetes complications and deaths in ethnic minority groups with T2DM.

5. DATA AND SAFETY MONITORING PLAN

The data and safety monitoring plan will include an internal Data Safety Monitoring Committee (DSMC) and the institutional IRB. The purpose of the DSMC and IRB are to ensure the safety of participants and the validity and integrity of the data. Summaries of adverse events reports or patient safety concerns raised by the IRB will be made to NIH in the yearly progress unless the nature of a particular event is such that it bears reporting to NIH immediately.

DSMC: The internal DSMC will consist of the PI, biostatistician, co-investigators/consultants on the proposal, and a designated medical monitor. The functions of the DSMC will include: 1) provide scientific oversight; 2) review all adverse effects or complications related to the study; 3) monitor accrual; 4) review summary reports relating to compliance with protocol requirements; and 5) provide advice on resource allocation. The DSMC will meet quarterly and as necessary by telephone. The recommendations of the DSMC will be reviewed and the PI will take appropriate corrective actions as needed.

Institutional IRB: The IRB will review and approve the funded protocol, review patient and provider consent forms, ensure protection of patient privacy and safety, and monitor the study on an ongoing basis. Adverse events will be reported to the IRB as they occur. Annual reports to the IRB will indicate accrual rate, adverse events, new findings that may influence continuation of the study, and reports of the DSMB.

INCLUSION OF CHILDREN

Children (ages 18-21) are included in this study. Children under the age of 18 years are excluded because type 2 diabetes is not common in younger aged children. Based on our study clinic demographics, we estimate that children 18-21 years will comprise ~5% of the sample.

INCLUSION OF WOMEN

Both men and women will be included in this study. Based on our study clinic demographics, we estimate that women will constitute 50% of the sample.

INCLUSION OF MINORITY GROUPS

Only minority adults (African Americans) are included in this study. This is justified because of the high burden of diabetes and its complication in African Americans, and the paucity of data on effective interventions in this population.

BIBLIOGRAPHY & REFERENCES CITED

